STUDY PROTOCOL AND STATISTICAL ANALYSIS PLAN

Full Title: Addressing Racial Disparities in Autism Diagnosis and Treatment: Translating Peer-to-Peer Support into a Clinical Setting

Institution: University of Maryland, Baltimore

NCT Identifier: NCT04313283

Unique Protocol ID: HP-00090447

Secondary ID: 1UL1TR003098

PI: [name]

Co-PI: [name]

Date Last Approved by Institutional Review Board: 09/01/2022 (original approval: 03/26/2020)

Justification, Objective, & Research Design

Specific Aims

Aim 1. Deliver Parents Taking Action to caregivers of Black children with developmental delays on a waitlist for an autism or developmental evaluation. Parent Leaders (parents of children 9+ years and older with autism) will deliver the program to 20 caregivers of waitlisted children (ages 8 and younger). We include children referred for autism or developmental concerns, as well as older children, due to concerns about late and/or inaccurate referrals of Black children.

Aim 2: Assess the feasibility, acceptability, and short-term outcomes of Parents Taking Action with a clinical sample. We will measure pre/post changes in child (challenging behaviors) and caregiver outcomes (parenting stress; depression; and family functioning, including social support); and evaluate intervention process measures (acceptability and fidelity). We hypothesize the intervention will be acceptable and feasible and improve child and caregiver outcomes.

Design

Phase 1: We will expand our advisory group to include Brown on the Spectrum (BOS) and SOM representatives and other relevant stakeholders. This group will advise us on local service needs and potential barriers and facilitators for implementation. We will continue to consult with this group throughout the research process.

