We will recruit potential intervention participants through local waitlists for a developmental or autism evaluation. (Children, particularly toddlers, who ultimately receive an autism diagnosis are often referred initially for developmental concerns.) To be eligible, participants must be the primary caregiver of a child eight years old or younger; and, identify their child as Black or African American. SOM clinical staff led by [name] will identify eligible children and their families from UMB's Developmental-Behavioral Pediatrics waitlist. We will also provide flyers to local providers, including general pediatricians, with [name] name (if providers can send a secure referral through Epic) or the research team information (for potential participants to contact the team directly). [name] will share the names and contact information of potential participants in a SharePoint Excel file only available to the research team which includes researchers from SOM and SSW. The research team will mail and email letters to potential participants the SOM clinical team identifies. The letter will provide the research team's contact information, and also notify the potential participants that a research team member will call them in the next week. All staff will follow strict protocols to protect the confidentiality of participant information, described in subsequent sections of this protocol. When the research team contacts potential participants, they will screen for the inclusion criteria described above before going through the informed consent and intake processes.

Research team staff will meet eligible potential participants in a private place and review the study information sheet in detail. Once the potential participant expresses comprehension of the risks and benefits of the research and agrees to participate, research staff will ask the participant to give verbal consent. The study staff will then request participants to complete baseline data (described below).

Participants will receive \$50 when they complete the questionnaires after completion of module 1 and another \$50 when they complete the final questionnaires and interview.

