NOTE: As needed, we will complete meetings and intervention delivery remotely. We will use secure video conferencing software (e.g., Webex, available through UMB) which allows phone-in or video joining options. For data collection, we will send participants secure Qualtrics links (a survey software available at UMB) to complete surveys. We will conduct and record interviews using video conferencing software (e.g., Webex).

Duration of Participation

Parent Leaders will be required to participate in 30-32 hours of training of Parents Taking Action Program, led by research staff. The Parent Leaders will work one-on-one with intervention participants to deliver two six-week modules (12 weeks total). Each Parent Leaders will be matched with approximately 4-5 caregivers each. Given it is not necessary for intervention participants' sessions to run concurrently, it is possible that Parent Leaders will deliver the intervention to their assigned caregivers through April 2021. We aim to hold the Parent Leaders post-intervention interviews in April 2021. These interviews will last approximately 60 minutes.

Three-time points measures (pre, post-module 1, and post-module 2) will take approximately one hour each for participants to complete. Post-intervention interviews with research staff will last approximately 60 minutes. We will use the same questionnaires for the three time points.

As noted above, as needed, we will hold the Parent Leader Training and intervention virtually.

Sample Size and Data Analysis

A convenience sampling method is appropriate for testing the feasibility and acceptability of this pilot trial. We aim to recruit additional 4 Parent Leaders and 20 intervention participants for this study. We will recruit potential intervention participants through waitlists for developmental or autism evaluations. (Children, particularly toddlers, who ultimately receive an autism diagnosis are often referred initially for developmental concerns.) To be eligible, participants must be the primary caregiver of a child eight years old or younger; and, identify their child as Black or African American.

Quantitative Data Analyses

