4. Post-intervention Interview Guides for Parent Leaders and Parent Leaders: 1 hour

Audio or Video Recording

We will audio record the post-intervention interviews to ensure we accurately capture their responses for our data analyses. Audio files will be saved using anonymous identifiers, rather than names or other identifiable information. Further, individuals will be instructed to not share their or their children's names in the interviews. The audio files will be professionally transcribed. Research staff will verify the transcript for accuracy and remove any identifying information that was unintentionally shared. Audio files will be deleted once transcripts are verified for accuracy.

Intervention Description

Parents Taking Action is an intervention originally developed to increase service access and knowledge among low-income Latino children with autism and their families (Magaña, Lopez, & Machalicek, 2017). In a previous study, we worked closely with our community advisory board to make cultural adaptations to the manual for use in Baltimore with a majority Black population. We adapted the program to deliver

content in two six-week modules (12 weeks total). The first module introduces topics on typical child development, autism and other developmental delays, common interventions and other methods to address child needs, parent stress and depression, and advocacy. The second module presents more advanced methods to improve social communication, reduce challenging child behaviors, and increase social support. We also provide participants with social work services to address challenging life circumstances, such as housing instability and food insecurity.

Participant Selection

The study is open to adults (18+) of any gender, race or ethnicity, provided they meet the inclusion criteria specified below. We will not target any vulnerable populations.

Inclusion Criteria:

1. [Parent Leaders Participant] Parent or other primary caregiver of a child age nine years or older with autism or other developmental disability
2. [Intervention Participant] Parent or other primary caregiver of a child age eight years or younger on waitlist for autism or developmental concerns
3. [All Participants] Identifies self or child as Black or African American

Recruitment

Intervention Participants

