Our research team will discuss the study with individuals who approach us directly through our flyers or through providers at the Developmental-Behavioral Pediatrics Clinic), or with those to whom we have sent an initial letter describing the study. We will explain that their participation is completely voluntary and then can withdraw from study at any time without penalty. Neither their participation in the study, nor a decision to withdraw, will not impact any services they may receive at the University of Maryland, Baltimore and/or University of Maryland Medical System. The statements regarding individuals' participation and right to withdraw are reiterated in the study information sheet, which will be reviewed with each participant.

Text of Advertisement

Maryland Parents Taking Action

Did you know that Black and African American children receive an autism diagnosis much later than white children?

This means that they often miss out on early intervention and other important services.

Parents Taking Action supports mothers, fathers and other primary caregivers in Maryland whose child is:

- Black or African American
- 8 years old or younger
- On the waitlist for an autism or developmental evaluation

Maryland PARENTS TAKING ACTION supports parents to develop skills to communicate and play with their children, manage challenging child behaviors, and advocate for needed services.

Maryland PARENTS TAKING ACTION is led by trained Parent Leaders, who themselves are parents of Black children with autism or other developmental disabilities.

The free program meets for two hours weekly for 12 weeks. It's one-on-one and meets when caregivers want!

Caregivers will receive up to \$100 for answering questions before, during and after they participate in the program, which will help us understand how the program is working.

If you a provider, please contact [name] through Epic to refer any potential participants.

If you are a caregiver, or want more information, please contact our study team at [contact] or call [contact].

Research Related Risks

When appropriate, we have listed the risks separately for intervention participants and Parent Leaders:

Risk for Intervention Participants

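### Does the looser race criterion in the formal inclusion list let in families outside the Aim 1 population?

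*Combined protocol and SAP*

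**What the plan says.** The race requirement for intervention participants appears in several places.

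- **Participant Selection, Inclusion Criteria.** Criterion 1 is labelled for Parent Leaders and criterion 2 for intervention participants. Criterion 3 covers both groups: "All Participants] Identifies self or child as Black or African American".
- **Intervention Participants Procedures, and again Sample Size and Data Analysis.** Both state that "participants must be the primary caregiver of a child eight years old or younger; and, identify their child as Black or African American".
- **Screening, also under Intervention Participants Procedures.** When staff contact potential participants, "they will screen for the inclusion criteria described above before going through the informed consent and intake processes".
- **Specific Aims, Aim 1.** The aim is to "Deliver Parents Taking Action to caregivers of Black children with developmental delays on a waitlist for an autism or developmental evaluation".
- **Text of Advertisement.** The flyer says that "Parents Taking Action supports mothers, fathers and other primary caregivers in Maryland whose child is", and the first item that follows is the child's race. It describes the Parent Leaders as people "who themselves are parents of Black children with autism or other developmental disabilities".

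The planned numbers are given under Sample Size and Data Analysis: "We aim to recruit additional 4 Parent Leaders and 20 intervention participants for this study".

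**The concern.** Race defines this study's population. The title concerns racial disparities in diagnosis, and Aim 1 justifies its broad age and referral limits by late or inaccurate referral of Black children. A reader who takes the list headed Inclusion Criteria as the governing text finds that either the caregiver's race or the child's is enough. A reader of the procedures section finds that only the child's race counts. A Black caregiver whose waitlisted child is not identified as Black is eligible on the first reading, ineligible on the second, and outside Aim 1.

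If the looser rule were the one applied, the pilot could describe a slightly different group from the one it set out to serve. With only 20 intervention participants planned, even a few such families would be a visible share of the sample. It is therefore reasonable to ask whether the conflict can affect who is enrolled or what is concluded.

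**Working it through.** The plan states no figure on this point, so there is none to reproduce. The check compares the two rules, asks which one operates at entry, and asks whether any analysis depends on the answer.

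**Step 1. Where the rules differ.** Call the formal list rule A (caregiver or child identified as Black) and the eligibility sentences rule B (child identified as Black).

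| Caregiver Black | Child Black | Rule A | Rule B | Same? |
|---|---|---|---|---|
| Yes | Yes | Eligible | Eligible | Yes |
| Yes | No | Eligible | Not eligible | No |
| No | Yes | Eligible | Eligible | Yes |
| No | No | Not eligible | Not eligible | Yes |

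Rule A admits three combinations and rule B admits two. They disagree on 3 − 2 = 1, the Black caregiver of a child not identified as Black. This counts logical cases, not families. The documents do not say how often that case occurs on the waitlists.

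**Step 2. How the rules combine.** Every combination admitted by B is also admitted by A. The rules are nested, so no one who satisfies B can fail A. A team that requires both admits (A and B) = B, which is the child-based population of Aim 1. Following the whole document therefore creates no impossible requirement, and the stricter sentence decides.

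**Step 3. Which rule operates at entry.** The screening sentence points to criteria stated above it. The eligibility sentence with the child-based rule stands earlier in that same section. The formal list comes later in the protocol, under Participant Selection, so the reference cannot mean that list. Families found through the clinic waitlist or provider referral are passed to the research team, which contacts and screens them. Families who respond to the flyer have read a child-based description, and under Informed Consent Process staff discuss eligibility with them before consent.

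**Step 4. Whether any result depends on it.** The Quantitative Data Analyses section bases the 20 families on alpha .05, an effect size of .3, parenting stress as the main outcome and 10% attrition. Race does not enter that basis. The GEE analysis describes change over time in parenting stress, depression, child behavior and family functioning. No race term, stratum or subgroup is planned. Making the two wordings agree would leave every one of these elements as it is.

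**Step 5. Size.** One family is 1/20 = 5% of the planned intervention participants. That is true of any single participant and does not measure this discrepancy. With screening on rule B, the expected number of discordant families enrolled is zero.

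**The case for a change.** The strongest case for a correction is that a list headed Inclusion Criteria should be the controlling text. The sentence that introduces Participant Selection says the study is open to those who meet that list. Criterion 3 is labelled for all participants, while the two criteria before it are group-specific, so on its face it governs intervention participants too. The Recruitment section has clinicians review the waitlist for eligible families without saying which wording they use. The background text under Importance of Knowledge to be Gained describes the population by the parents' race. Rewording one criterion would be cheap.

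Part of this stands. The wordings differ, the label does reach intervention participants, and no sentence reconciles them. The rest carries less weight. Waitlist review only produces names for the research team, and the child-based screen comes afterwards. The background sentence is a statement of importance, not an entry rule.

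The obvious edit also has a cost. Removing the reference to the participant's own race from the shared line would narrow eligibility for Parent Leaders, since a Black Parent Leader whose child is not identified as Black now qualifies. No eligibility text for Parent Leaders conflicts with criterion 3. Only the flyer describes them as parents of Black children, and a flyer is not an eligibility list. A plausible reading is that the line was worded broadly because it had to serve both groups.

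**Conclusion.** The inconsistency is real but clerical, and no change to the plan is needed. The looser wording sits in a line shared by two groups. The specific sentences for intervention participants, the screening step, Aim 1 and the flyer all use the child's race. Because the child-based rule lies wholly within criterion 3, following the plan as written enrols the intended population. The sample size, the analysis and the interpretation of the pre/post changes stay the same.

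The conclusion assumes that the screening call is carried out as described and that staff read its reference as pointing to the earlier text in the same section. If some staff worked from the formal list alone, a few families outside Aim 1 could enter. The documents give no basis for estimating how many. Even then, the planned analyses would run unchanged, and the effect would be confined to how the sample is described.
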